#### 4.8.4. Electrocardiogram

Tabulation of actual value and change from baseline to each on study evaluation will be presented for all continuous ECG measurements (heart rate, PR interval, QRS interval, QT interval). No hypothesis testing will be conducted for vital sign data.

ECG results will also be summarized by the number and percent of subjects with overall normal, abnormal and clinically significant abnormal results at baseline and each study visit.

All ECG data for each subject will be provided in data listings.

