7.5 Statistical Analysis of Safety Data

The primary safety endpoint is the proportion of subjects with at least 1 AE comparing individual PTG-100 dosing groups with placebo.

The secondary endpoints (all based on comparison of individual PTG-100 dose levels to placebo) will include:

1. Frequency and type of AEs (affecting $\geq 5\%$ of subjects)
2. Proportion of subjects with at least 1 SAE
3. Number and type of SAEs
4. Frequency of AEs of special interest including serious or opportunistic infection (viral, bacterial, fungal including systemic/gut localization), allergic/drug reactions, immune system disorders, and suspected PML
5. Clinically significant changes in safety labs, ECGs, or physical examination findings (including vital signs).

Continuous safety data will be summarised with descriptive statistics (arithmetic mean, standard deviation [SD], median, minimum, and maximum) by dose level. Categorical safety data will be summarised with frequency counts and percentages by dose level. Adverse events will be coded using the most current Medical Dictionary for Regulatory Activities available, which will be indicated in the Data Management Plan. A by-participant AE data listing, including verbatim term, preferred term, system organ class, treatment, severity, and relationship to study drug, will be provided. The number of participants experiencing treatment-emergent AEs (TEAEs) and number of individual TEAEs will be summarised by treatment group, system organ class, and preferred term. The TEAEs will also be summarised by severity and by relationship to study drug.

Laboratory evaluations, vital signs assessments, and ECG parameters will be summarised by treatment group and protocol-specified collection time point. A summary of change-

from-baseline at each protocol-specified time point by treatment group will also be presented.

Clinically significant changes in physical examinations will be listed for each participant and described in the text of the Clinical Study Report.

Medical history will be listed by subject.

Concomitant medications will be listed by participant and coded using the most current World Health Organization drug dictionary.

Further details regarding presentation and analysis of safety data will be detailed in the SAP.

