### 4.8.1. Adverse Events

The primary safety endpoint is the proportion of subjects with at least 1 AE comparing individual PTG-100 dose groups with placebo.

Secondary endpoints (all based on comparison of individual PTG-100 dose levels to placebo) will include:

- Frequency and type of AEs (affecting  $\geq 5\%$  of subjects)
- Proportion of subjects with at least 1 SAE
- Number and type of SAEs
- Frequency of adverse events of special interest (AESI) including serious or opportunistic infection (viral, bacterial, fungal including systemic/ gut localization), allergic/ drug reactions, immune system disorders, and PML or new onset neurologic symptoms

Adverse events will be coded using the Medical Dictionary for Regulatory Activities (MedDRA) and displayed in tables and listings using System Organ Class (SOC) and Preferred Term.

Analyses of adverse events will be performed for those events that are considered treatment emergent, where treatment emergent is defined as any adverse event with onset after the administration of study medication through the end of the study visit or any event that was present at baseline but worsened in intensity or was subsequently considered drug-related by the investigator through the end of the study.

Adverse events are summarized by subject incidence rates, therefore, in any tabulation, a subject contributes only once to the count for a given adverse event (SOC or preferred term).

The number and percentage of subjects

- with any treatment-emergent adverse event
- with any treatment-emergent adverse events assessed by the Investigator as related to treatment (definite, probable, or possible relationship)
- with any treatment-emergent serious adverse event
- with treatment-emergent adverse events by severity
- with adverse events affecting  $\geq 5\%$  of subjects within any treatment group across both stages of the study
- with AESI

will be summarized by treatment group and overall. In addition, all active groups will be pooled in the summaries for comparison to placebo. In these tabulations, each subject will contribute

only once (i.e., the most related occurrence or the most intense occurrence) to each of the incidence rates in the descriptive analysis, regardless of the number of episodes.

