#### 4.8.3. Vital Signs and Physical Examinations

Tabulation of actual value and change from baseline to each on study evaluation will be presented for all vital signs. No hypothesis testing will be conducted for vital sign data.

By-subject listings of vital sign measurements will be presented in data listings.

Physical examination results at each time point will be summarized; shifts from baseline in physical examination findings to each on study visit will also be presented. Clinically significant changes in physical examinations will be listed for each participant and described in the text of the final report.

A tabulation (n, %) of subjects with a physical examination abnormality will be presented by visit and dose group. The tabulation will be presented by body system. Subjects with no examination for a particular body system will not be included in the summary statistics for that body system. No formal statistical comparisons will be performed.

All physical examination findings will be presented in a data listing.

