Table 14.3.1.8	Summary of Adverse Events Leading to Study Withdrawal by System Organ Class, Preferred Term and Treatment Group (Safety)
Table 14.3.1.9	Summary of Treatment-Emergent Adverse Events with a Fatal Outcome by System Organ Class, Preferred Term and Treatment Group (Safety)

*Listings of Deaths, Serious Adverse Events and Other Significant Events (CSR Section 14.3.2)*

Table 14.3.2.1	Listing of Subject Deaths
Table 14.3.2.2	Listing of Serious Adverse Events
Table 14.3.2.3	Listing of Adverse Events Leading to Withdrawal or Death

*Abnormal Laboratory Value Tables and Listings (CSR Section 14.3.4)*

Table 14.3.4.1.1	Summary of Clinical Laboratory Abnormalities: Hematology (Safety)
Table 14.3.4.1.2	Summary of Clinical Laboratory Abnormalities: Chemistry (Safety)
Table 14.3.4.1.3	Summary of Clinical Laboratory Abnormalities: Urinalysis (Safety)
Table 14.3.4.1.4	Summary of Clinical Laboratory Abnormalities: Coagulation (Safety)
Table 14.3.4.2.1	Listing of Clinical Laboratory Abnormalities: Hematology (Safety)

Table 14.3.4.2.2	Listing of Clinical Laboratory Abnormalities: Chemistry (Safety)
Table 14.3.4.2.3	Listing of Clinical Laboratory Abnormalities: Urinalysis (Safety)
Table 14.3.4.2.4	Listing of Clinical Laboratory Abnormalities: Coagulation (Safety)

*Other Safety Information (CSR Section 14.4)*

Table 14.4.1.1	Clinical Laboratories: Hematology Actual Values and Changes Over Time on Study (Safety Population)
Table 14.4.1.2	Clinical Laboratories: Chemistry Actual Values and Changes Over Time on Study (Safety Population)
Table 14.4.1.3	Clinical Laboratories: Urinalysis Actual Values and Changes Over Time on Study (Safety Population)
Table 14.4.1.4	Clinical Laboratories: Coagulation Actual Values and Changes Over Time on Study (Safety Population)
Table 14.4.2.1	Clinical Laboratories: Shifts from Baseline Over Time on Study for Hematology (Safety Population)
Table 14.4.2.2	Clinical Laboratories: Shifts from Baseline Over Time on Study for Clinical Chemistry (Safety Population)
Table 14.4.2.1	Clinical Laboratories: Shifts from Baseline Over Time on Study for Urinalysis (Safety Population)
Table 14.4.2.2	Clinical Laboratories: Shifts from Baseline Over Time on Study for Coagulation (Safety Population)
Table 14.4.3	Vital Signs: Actual Values and Changes Over Time on Study (Safety Population)
Table 14.4.4	Shifts from Baseline Over Time on Study for Physical Examination Findings (Safety Population)

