Table 14.4.5	Electrocardiogram Results: Actual Values and Changes Over Time on Study (Safety Population)
Table 14.4.6	Concomitant Medications (Safety Population)
Table 14.4.7	Summary of Physical Examinations

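### SAP 4.8.1 omits the protocol's fifth secondary safety endpoint without declaring it, and no planned table counts new clinically significant ECG or vital-sign changes by arm

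*SAP*

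**What the plan says.** Protocol 7.5 (and the synopsis) lists five secondary safety endpoints, all as comparisons of individual dose levels with placebo. The fifth is "Clinically significant changes in safety labs, ECGs, or physical examination findings (including vital signs"). Further down, the same section describes the analysis: "Laboratory evaluations, vital signs assessments, and ECG parameters will be summarised by treatment group and protocol-specified collection time point", together with change from baseline.

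SAP 4.8.1 opens its list with "Secondary endpoints (all based on comparison of individual PTG-100 dose levels to placebo) will include" and then gives four items, the last being adverse events of special interest. The fifth protocol endpoint is not there. SAP 5 states that nothing has changed from the protocol-defined analyses.

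For ECGs, SAP 4.8.4 plans two things:
- "Tabulation of actual value and change from baseline to each on study evaluation will be presented for all continuous ECG measurements" (heart rate, PR, QRS, QT);
- overall results "summarized by the number and percent of subjects with overall normal, abnormal and clinically significant abnormal results at baseline and each study visit".

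The only ECG table listed in SAP 7.1 is Table 14.4.5, "Electrocardiogram Results: Actual Values and Changes Over Time on Study (Safety Population").

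For vital signs, SAP 4.8.3 says "Tabulation of actual value and change from baseline to each on study evaluation will be presented for all vital signs", plus by-subject listings. The only table is 14.4.3, "Vital Signs: Actual Values and Changes Over Time on Study (Safety Population").

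**The concern.** Safety and tolerability is one of the two primary objectives. A secondary safety endpoint that the protocol states should be either reported or openly withdrawn. Here it is absent from the SAP's list while the SAP declares no change, and for two of its components the planned output does not yield the quantity.

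The endpoint is about change. A percentage at baseline beside a percentage at each visit nets new findings against resolved ones, and it forms no per-subject incidence across visits. Continuous summaries of vital signs show location, spread and extremes. They do not show how many subjects in each arm had a clinically significant change that was absent at baseline. A reader of the study report would have to rebuild both counts from listings, and for vital signs would have to choose a criterion after seeing the data.

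**Working it through.** The plan states no figure for this point, so there is none to reproduce. The check is a comparison of texts, followed by a short calculation of what separate percentages can and cannot reveal.

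**Step 1. Component by component, SAP 4.8.2 to 4.8.4 and the table list in SAP 7.1**

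| Component of endpoint 5 | Linked to the subject's baseline? | Count of affected subjects? |
|---|---|---|
| Laboratory | Yes: change from baseline and shift tables (14.4.2.x) | Yes: by treatment group, abnormality at any time (14.3.4.1.x) |
| Physical examination | Yes: shifts (14.4.4) | Yes: abnormalities by visit and dose group; clinically significant changes listed |
| ECG intervals and heart rate | Yes: change from baseline (14.4.5) | No |
| ECG overall category | No: percentages at baseline and each visit | Per visit only; no new-onset count, no shift table |
| Vital signs | Change from baseline (14.4.3), with mean, median, SD, minimum and maximum under SAP 4.2.1 | No |

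The gap is therefore confined to the ECG category and vital signs.

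**Step 2. What the ECG percentages determine**

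Take *n* subjects with an ECG at both times, *a* in the category at baseline and *b* at a visit. The number who are new at that visit is only known to lie between

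max(0, *b* − *a*) and min(*b*, *n* − *a*).

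SAP 2.1 expects about 70 to 80 subjects per selected arm. The category counts below are assumptions.

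| *n* | *a* | *b* | New cases compatible with the table |
|---|---|---|---|
| 80 | 4 | 4 | 0 to 4 |
| 80 | 8 | 8 | 0 to 8 |
| 70 | 7 | 7 | 0 to 7 |
| 80 | 8 | 12 | 4 to 12 |

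A single case shows the mechanism. Of 75 subjects, 8 are in the category at baseline, 4 of them resolve and 4 others enter. The table shows 8/75 = 10.7% at baseline and (8 − 4 + 4)/75 = 10.7% at the visit. Yet 4 of the 75 − 8 = 67 subjects without the finding at baseline, or 6.0%, acquired it.

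**Step 3. Across visits**

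On-treatment ECGs are scheduled on Days 14, 56 and 84. Suppose 3% of subjects are newly affected at each visit. The share ever affected is 3% if they are always the same subjects, 1 − 0.97³ = 8.7% if visits are independent, and 3 × 3% = 9% if no subject recurs. The planned table shows 3% three times in every case.

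**Step 4. Day 112**

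Footnote 9 of the schedule (Protocol Table 6-1, SAP Table 1) restricts the Day 112 ECG to subjects with an earlier abnormal one. That visit's percentage has a selected denominator and cannot be set beside the baseline percentage.

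**Step 5. Is the missing information collected?**

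For ECGs, yes: Protocol 6.13.5 has the investigator's overall interpretation recorded in the CRF. For vital signs the measurements are collected, including 1, 2 and 4 hours after the first dose, but neither document defines what counts as a clinically significant change.

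**The case against.** The strongest reply has four parts.

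*SAP 4.8.1 is the adverse event section, so a non-event endpoint naturally moves to the later sections.* This largely holds for laboratory and examination data, which are well covered there. It does not hold for the ECG category or vital signs, and nothing in those later sections identifies their output as the protocol's fifth endpoint.

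*The protocol never promised these tables.* Endpoint 5 names no summary measure, and the protocol's analysis paragraph asks only for summaries by time point and change from baseline, which the SAP delivers. That is correct, and the exact layout is a matter of choice. The paragraph does not cancel the endpoint listed above it, though, and it leaves further detail to the SAP.

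*Clinically significant changes reach the adverse event tables, counted once per subject and treatment-emergent, so the link to baseline exists.* This is the best argument. Protocol 6.13.6 makes significant examination findings adverse events. Protocol 6.13 groups vital signs with the examination, and the general definition in Appendix F could take in an ECG change. But Protocol 6.13.4 and 6.13.5 contain no such rule for vital signs or ECGs, so capture is not assured. Events that are captured would be spread over separate preferred terms and not totalled as this endpoint.

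*The illustrations use invented rates, and the exclusions for cardiovascular disease should keep significant baseline ECGs few.* Both points are fair. If *a* is near zero, the percentage at a visit is close to the new-onset rate at that visit. The problem of combining visits in Step 3 remains.

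A reader might also infer that the SAP abandons the endpoint altogether, or that vital signs are reported only as means. The documents support neither: two components keep baseline-linked output, and SAP 4.2.1 adds median, SD, minimum and maximum.

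**Conclusion.** The point holds in a limited form. The fifth secondary safety endpoint is missing from the SAP's list and the omission is not declared. For ECGs and vital signs, no planned table gives the number of subjects per arm with a new clinically significant change from baseline. Adverse event reporting may capture some of these, but not as this endpoint.

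It would go too far to say that such changes are never counted, or that the safety evaluation fails. Laboratory and examination changes are tabulated, ECG intervals have change from baseline, all ECG and vital-sign data are listed, and the primary safety endpoint (at least one adverse event) and the efficacy analyses are untouched.

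The size cannot be estimated from the documents because they give no ECG or vital-sign abnormality rates. The ranges above show only that the planned ECG table does not determine the count: 0 to 8 new cases for 8 and 8 of 80, under assumed counts and with an ECG from every subject at both times. This should be corrected before unblinding. It is inexpensive, and without it the trial cannot report, from its planned tables, an endpoint that it states.

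**What to change.** 1. Restore endpoint 5 to the SAP's secondary safety endpoints and point to the tables that report each component. If leaving it out was intended, say so in SAP 5 with the reason.
2. For ECGs, add a shift table by arm of baseline category against the category at each visit and against the worst on-treatment category. Add the number and percentage per arm with a new clinically significant abnormality among subjects without one at baseline. Both use the investigator interpretation already recorded. Mark Day 112 as a selected subset.
3. For vital signs, add the number and percentage per arm with a new clinically significant change from baseline, under a criterion that the sponsor fixes before unblinding.

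The cost is SAP wording and about three tables. The ECG output needs no new data. The vital-sign count needs no new measurements, but it does need a criterion that neither document contains at present.

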#### 4.8.5. Concomitant Medications

Concomitant medications will be coded using the WHO Drug dictionary. Results will be tabulated by Anatomic Therapeutic Class (ATC) and preferred term.

The use of concomitant medications will be included in by-subject data listing.

## **5. CHANGES TO PLANNED ANALYSES**

As of this date, there have been no changes between the protocol-defined statistical analyses and those presented in this statistical plan.

## **7. CLINICAL STUDY REPORT APPENDICES**

### **7.1. Statistical Tables to be Generated**

#### *Disposition/Demographics/Baseline/Exposure (CSR Table Section 14.1)*

Table 14.1.1.1	Subject Enrollment and Disposition (All Subjects)
Table 14.1.1.2	Subject Disposition by Visit (FAS)
Table 14.1.2	Demographic and Baseline Characteristics (Safety Population)
Table 14.1.3	Baseline Disease Characteristics (Safety Population)
Table 14.1.4	Medical History (Safety Population)
Table 14.1.5	Physical Examination at Screening (Safety Population)
Table 14.1.6	Exposure to Study Treatment (Safety Population)

#### *Efficacy/Pharmacokinetic Results (CSR Table Section 14.2)*

Table 14.2.1.1A	Proportion of Subjects with Clinical Remission at Week 12 (FAS)
Table 14.2.1.1B	Proportion of Subjects with Clinical Remission at Week 12 (PP)
Table 14.2.1.2A	Proportion of Subjects with Clinical Remission at Week 12 by Prior TNF-alpha Use (FAS)
Table 14.2.1.2B	Proportion of Subjects with Clinical Remission at Week 12 by Prior TNF-Alpha Use (PP)
Table 14.2.1.3A	Proportion of Subjects with Endoscopic Response at Week 12 (FAS)
Table 14.2.1.3B	Proportion of Subjects with Endoscopic Response at Week 12 (PP)
Table 14.2.1.4A	Proportion of Subjects with Clinical Response at Week 12 (FAS)
Table 14.2.1.4B	Proportion of Subjects with Clinical Response at Week 12 (PP)
Table 14.2.1.5A	Proportion of Subjects with Endoscopic Remission at Week 12 (FAS)
Table 14.2.1.5B	Proportion of Subjects with Endoscopic Remission at Week 12 (PP)
Table 14.2.2.1A	Change in complete Mayo Score from Baseline to Week 12 (FAS)

Table 14.2.2.1B	Change in complete Mayo Score from Baseline to Week 12 (PP)
Table 14.2.2.1C	Change in complete Mayo Score from Baseline to Week 12 (Sensitivity Analyses - if Needed)
Table 14.2.2.2A	Change in Partial Mayo Score from Baseline Over Time (FAS)
Table 14.2.2.2B	Change in Partial Mayo Score from Baseline Over Time (PP)
Table 14.2.2.2C	Change in Partial Mayo Score from Baseline Over Time (Sensitivity Analyses - if Needed)
Table 14.2.2.3A	Change in Endoscopy Subscore from Baseline to Week 12 (FAS)
Table 14.2.2.3B	Change in Endoscopy Subscore from Baseline to Week 12 (PP)
Table 14.2.2.3C	Change in Endoscopy Subscore from Baseline to Week 12 (Sensitivity Analyses – if Needed)
Table 14.2.2.4A	Change in Rectal Bleeding Subscore from Baseline Over Time (FAS)
Table 14.2.2.4B	Change in Rectal Bleeding Subscore from Baseline Over Time (PP)
Table 14.2.2.4C	Change in Stool Frequency Subscore from Baseline Over Time (Sensitivity Analyses – if Needed)
Table 14.2.2.5A	Change in Stool Frequency Subscore from Baseline Over Time (FAS)
Table 14.2.2.5B	Change in Stool Frequency Subscore from Baseline Over Time (PP)
Table 14.2.2.5C	Change in Stool Frequency Subscore from Baseline Over Time (Sensitivity Analyses – if Needed)
Table 14.2.2.6A	Change in Fecal Calprotectin Levels from Baseline Over Time (FAS)
Table 14.2.2.6B	Change in Fecal Calprotectin Levels from Baseline Over Time (PP)
Table 14.2.2.6C	Change in Fecal Calprotectin Levels from Baseline Over Time (Sensitivity Analyses – if Needed)
Table 14.2.2.7A	Change in IBDQ score from Baseline Over Time (FAS)
Table 14.2.2.7B	Change in IBDQ score from Baseline Over Time (PP)

Table 14.2.2.7C	Change in IBDQ score from Baseline Over Time (Sensitivity Analyses – if Needed)
Table 14.2.2.7A	Change in Histological score from Baseline Over Time (FAS)
Table 14.2.2.7B	Change in Histological score from Baseline Over Time (PP)
Table 14.2.3	Summary of Pharmacokinetic Parameters (PK Population)
Table 14.2.4.1A	Change in $\alpha 4\beta 7$ Receptor Occupancy on Peripheral Blood T cells Over Time (FAS)
Table 14.2.4.1B	Change in $\alpha 4\beta 7$ Receptor Occupancy on Peripheral Blood T cells Over Time (PP)
Table 14.2.4.2A	Summary of $\alpha 4\beta 7$ Receptor Expression on Peripheral Blood T cells Over Time (FAS)
Table 14.2.4.2B	Summary of $\alpha 4\beta 7$ Receptor Expression on Peripheral Blood T cells Over Time (PP)
Table 14.2.4.3A	Change in Peripheral Blood Lymphocytes Over Time (FAS)
Table 14.2.4.3B	Change in Peripheral Blood Lymphocytes Over Time (PP)
Table 14.2.4.4A	Change in $\beta 7$ Positive Cells in Colonic Biopsies Over Time (FAS)
Table 14.2.4.4B	Change in $\beta 7$ Positive Cells in Colonic Biopsies Over Time (PP)
Table 14.2.5.1A	Proportion of Subjects with Positive Neutralizing ADA by Week 12 and Week 16 (FAS)
Table 14.2.5.1B	Proportion of Subjects with Positive Neutralizing ADA by Week 12 and Week 16 (PP)

*Displays of Adverse Events (CSR Section 14.3.1)*

Table 14.3.1.1	Overall Summary of Treatment-Emergent Adverse Events by Treatment Group (Safety)
Table 14.3.1.2	Summary of Treatment-Emergent Adverse Events by System Organ Class, Preferred Term and Treatment Group, Sorted in Descending Frequency according to the Total Column (Safety)

Table 14.3.1.3	Summary of Related/Possibly, Probably and Definitely Related Treatment-Emergent Adverse Events by System Organ Class, Preferred Term and Treatment Group (Safety)
Table 14.3.1.4	Summary of Treatment-Emergent Adverse Events by Severity, System Organ Class, Preferred Term and Treatment Group (Safety)
Table 14.3.1.5	Summary of Treatment-Emergent Serious Adverse Events by System Organ Class, Preferred Term and Treatment Group (Safety)
Table 14.3.1.6	Summary of Most Common ( $\geq 5\%$ within any treatment group) Treatment-Emergent Adverse Events by System Organ Class, Preferred Term and Treatment Group (Safety)
Table 14.3.1.7	Summary of Treatment-Emergent Adverse Events by Preferred Term and Treatment Group (Safety)
Table 14.3.1.8	Summary of Adverse Events Leading to Study Withdrawal by System Organ Class, Preferred Term and Treatment Group (Safety)
Table 14.3.1.9	Summary of Treatment-Emergent Adverse Events with a Fatal Outcome by System Organ Class, Preferred Term and Treatment Group (Safety)

*Listings of Deaths, Serious Adverse Events and Other Significant Events (CSR Section 14.3.2)*

Table 14.3.2.1	Listing of Subject Deaths
Table 14.3.2.2	Listing of Serious Adverse Events
Table 14.3.2.3	Listing of Adverse Events Leading to Withdrawal or Death

*Abnormal Laboratory Value Tables and Listings (CSR Section 14.3.4)*

Table 14.3.4.1.1	Summary of Clinical Laboratory Abnormalities: Hematology (Safety)
Table 14.3.4.1.2	Summary of Clinical Laboratory Abnormalities: Chemistry (Safety)
Table 14.3.4.1.3	Summary of Clinical Laboratory Abnormalities: Urinalysis (Safety)
Table 14.3.4.1.4	Summary of Clinical Laboratory Abnormalities: Coagulation (Safety)
Table 14.3.4.2.1	Listing of Clinical Laboratory Abnormalities: Hematology (Safety)

Table 14.3.4.2.2	Listing of Clinical Laboratory Abnormalities: Chemistry (Safety)
Table 14.3.4.2.3	Listing of Clinical Laboratory Abnormalities: Urinalysis (Safety)
Table 14.3.4.2.4	Listing of Clinical Laboratory Abnormalities: Coagulation (Safety)

*Other Safety Information (CSR Section 14.4)*

Table 14.4.1.1	Clinical Laboratories: Hematology Actual Values and Changes Over Time on Study (Safety Population)
Table 14.4.1.2	Clinical Laboratories: Chemistry Actual Values and Changes Over Time on Study (Safety Population)
Table 14.4.1.3	Clinical Laboratories: Urinalysis Actual Values and Changes Over Time on Study (Safety Population)
Table 14.4.1.4	Clinical Laboratories: Coagulation Actual Values and Changes Over Time on Study (Safety Population)
Table 14.4.2.1	Clinical Laboratories: Shifts from Baseline Over Time on Study for Hematology (Safety Population)
Table 14.4.2.2	Clinical Laboratories: Shifts from Baseline Over Time on Study for Clinical Chemistry (Safety Population)
Table 14.4.2.1	Clinical Laboratories: Shifts from Baseline Over Time on Study for Urinalysis (Safety Population)
Table 14.4.2.2	Clinical Laboratories: Shifts from Baseline Over Time on Study for Coagulation (Safety Population)
Table 14.4.3	Vital Signs: Actual Values and Changes Over Time on Study (Safety Population)
Table 14.4.4	Shifts from Baseline Over Time on Study for Physical Examination Findings (Safety Population)
Table 14.4.5	Electrocardiogram Results: Actual Values and Changes Over Time on Study (Safety Population)
Table 14.4.6	Concomitant Medications (Safety Population)
Table 14.4.7	Summary of Physical Examinations

